### Programming Note:

1. This output will be repeated for different subsets of patients.
2. MDASI was only collected for Metastatic patients, so only display the Metastatic column.
3. Percentages should be based upon the small n.
4. 30% reductions is any 30% reduction in a given analysis variable. See titles and footnotes in the lopo for these different reduction criteria.
5. N is the number of patients within the specific population.
6. Only include the questions for Disease Related Symptoms.
7. If a subject has had a reduction for the given criteria (see 30% reduction note) then they would appear in 'yes' and not in 'no'.

## Output Specifications: Efficacy Tables

Best Response:

1) Best Confirmed overall response.

RSPT01	
Output ID: t_rs_best_*
 

● Analysis Population: Patients with measurable disease at baseline, excluding patients without histologically confirmed BCC. Outputs will be repeated for different population combinations - please see the LoPO for details of these combinations, and the Efficacy Population section for details on populations.

● Column Variables: Disease Status (Locally Advanced, Metastatic)

● Column Totals: Totals of non-missing Disease Status

● Analysis Variables: Response variable is the Best Overall Response: Complete Response, Partial Response, Stable Disease, Progressive Disease, Not evaluable, or Missing.

● Statistics and Calculation Methods: Use proq freq.

○ Display Patients with histologically-confirmed measurable disease at baseline

○ CIs for Best Overall Response Rate presented in the table are displayed as percentages, i.e. the actual values multiplied by 100.

○ <math>\alpha</math> level for CIs is 2-sided 5%.

○ Method of Clopper-Pearson is to be used to derive 95% CI for proportion.

● Numeric Precision and Formatting of Statistics: Use standard display in the mockup

● Optional Subsetting: Display Response categories i.e. Complete Response, Partial Response, Stable Disease, Progressive Disease, Missing, or Not evaluable, are displayed with percentage.

---------------	--

Programming Notes:

- Best Overall Response (BOR) would be Complete Response (CR) if subject had CR on each of two tumor assessments which are greater than or equal to 23 days apart (with either no other tumor assessments in between or the tumor response between these two assessments is CR or Not Evaluable (NE)).

- Best Overall Response would be Partial Response (PR) if subject's best overall response is not CR and the subject had two tumor assessments greater than or equal to 23 days apart with the response of the first assessment being PR and the second being PR or CR (with either no other tumor assessments in between or the tumor response between these two assessments being CR, PR, or NE).
- Best Overall Response would be Stable Disease (SD) if subject's best overall response is not CR or PR, and there is at least one response assessment of CR, PR or SD with minimum of 51 days after First Dose Date without any Progressive Disease (PD) in between.
- Best Overall Response would be Progression Disease (PD) if subject's best overall response is not CR, PR, or SD, and if there is at least one response assessment of PD.
- Best Overall Response would be Not Evaluable (NE) if subject's best overall response is not CR, PR, SD, or PD, and there is at least one response assessment of NE.
- BOR would be PD if PD occurred before satisfying any of the above criteria of Best Overall Response.
- Patients who achieve best overall response of CR or PR are considered a responder.
- Best overall response rate is defined as the number of patients with a CR or PR observed at two consecutive assessments  $\geq 4$  weeks apart ( $\geq 23$  days) divided by the total number of patients with histologically confirmed measurable disease at baseline.
- N in column headings is the number of patients with a measurable or non-measurable disease at baseline and histologically confirmed BCC. Percentages are calculated based on the number of patients with a measurable disease at baseline and histologically confirmed BCC.
- Display only Responder and 95%CI for Best Overall Response Rate.

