Record Date of Last Menses ¹¹	X	X	X	X	X	X	X	X	X	X	X
Pregnancy Test ¹²	X	X	X	X	X	X	X	X	X	X	
Serum Hormone Evaluation ¹³	X	As clinically indicated								As clinically indicated	As clinically indicated
Steady-state and post-treatment pharmacokinetic collection of blood (AT SELECTED SITES ONLY) ²⁴		One collection while taking vismodegib for at least 2 weeks continuously									At 3, 6, 9, and 12 Months ONLY
QoL Assessments using Skindex-16 (in selected sites)	X		X					X		X	

Table 1 Schedule of Assessments (cont.)

Cycle	Screening / Baseline	Treatment Phase ¹ (Allowed Visit Window +/- 3 days from Cycle 2 onwards)								End of Treatment Visit ²	Safety Follow-Up Visits ³ (1 month, 3 months, 6 months, 9 months, 12 months after the last dose of vismodegib (GDC-0499))
		1	2	3	4	5	6	7	8 onwards		
Day	-28 to -1	1	29	57	85	113	141	169	Every 28 Days		
Symptom Assessment using MDASI ¹⁴	X	X	X	X	X	X	X	X	X	X	X
Tumor Assessments (physical examination) ^{15, 17}	X	Every 4 to 8 weeks from the time of the first dose (±5 days) regardless of dosing delays.								X	
Tumor Assessments (by imaging techniques, if required) ^{16, 17}	X	Every 8 to 16 weeks from the time of the first dose (±5 days) regardless of dosing delays or as per institutional standards In metastatic BCC patients (newly enrolled after approval of the Study Protocol, version 4.0), every 8 weeks from time of first dose (±5 days) regardless of dosing delay								X	
AEs / SAEs ¹⁸	X	X								X	X
AE-related pharmacokinetic collection of blood (AT SELECTED SITES ONLY) ²⁵											At 6, 9, and 12 Months ONLY
Ultrasound ¹⁹	X	As clinically indicated								As clinically indicated	As clinically indicated
Follow-up for disease progression		X								X	X
Tumor biopsy and collection of whole blood ²⁰										X	
Concomitant medication	X ²¹	X								X	X
New anti-cancer therapy										X	X
Drug Dispensing		X (first day of each Cycle)									
Drug Accountability ²² Drug Dosing Exception Diary ²³			X	X	X	X	X	X	X	X	X

Table 1 Schedule of Assessments (cont.)

Notes Results of screening tests or examination performed as standard of care before obtaining informed consent and within the specified interval may be used rather than repeating required evaluation. Day 1 = first dose of study drug vismodegib.

1. Visits during the treatment period are to be completed on Day 1 of every 28-Day Cycle.
2. End of Treatment Visit will be performed when the patient discontinues vismodegib regardless of when it occurs.

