institutional standards (see below). For a list of study assessments, see the Study Flowchart ([Table 1. Schedule of Assessments](#)).

Assessment of safety, the primary objective of this trial, will occur by examining the incidence, type, and severity of AEs; the incidence and nature of serious AEs (SAEs); the incidence of AEs leading to vismodegib discontinuation or interruption; and the cause of death on study (if not linked to disease progression).

The pharmacokinetics of vismodegib will be assessed in an exploratory manner at selected sites. Adverse event-related PK testing will be performed on patients having any adverse events that were reported as being related to vismodegib treatment and that continued for at least 6 months after the last dose of vismodegib. This PK sample collection will occur at 6 months, 9 months, and 12 months after the last dose of vismodegib (± 5 days). In addition, post-treatment PK testing will be performed on 30 patients to further characterize the post-treatment elimination of vismodegib from steady-state exposure to 12 months after the last dose of vismodegib, with PK sample collection occurring at 3 months, 6 months, 9 months, and 12 months after the last dose of vismodegib (± 5 days).

Efficacy will be assessed according to RECIST, v1.1. Measurable tumors accessible to evaluation by physical examination should be assessed within a maximum of 7 days prior to the first dose of study drug (baseline reading) and every 4 to 8 weeks thereafter. If assessment requires imaging, baseline CT and/or MRI should be performed within a maximum of 28 days prior to the first dose of study drug and, if such scans demonstrate evidence of disease, follow-up imaging studies (CT and/or MRI) should be performed every 8 to 16 weeks or as per institutional standards from the time of the first dose, regardless of dosing delays. Other imaging techniques may be performed as clinically indicated, but should not be used for determining tumor response. Objective responses using RECIST, v1.1 should be confirmed by repeat assessments at least 4 weeks after initial documentation of response.

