5.3.6 Tumor Response Criteria

Tumor response will be evaluated according to the RECIST, v1.1 criteria ([Appendix 1](#)). The majority of patients in this study have locally advanced BCC and in this disease setting measurable tumors are accessible to evaluation by physical examination. This study allows for more than two target skin lesions, which takes into account patient with multiple BCC.

In this study, tumor response will be measured for patients with measurable disease by physical examination and/or imaging (CT and/or MRI scans), at the Investigator's discretion. Other imaging techniques may be performed as clinically indicated, but should not be used for determining tumor response. For each patient, the same method of assessment and the same technique **must** be used to evaluate each lesion throughout the entire study. If more than one method is used, the most accurate method according to RECIST should be selected when recording data.

Patients with non-measurable disease should be assessed for disease progression when clinically indicated and in accordance with standard clinical practice. For metastatic patients, assessment of non-measurable disease should be carried out according to RECIST, version 1.1.

For both metastatic and locally advanced BCC cohorts, a new cutaneous BCC will be considered as PD if the lesion is >5 mm and can be clearly documented as not being previously present, unless it is confirmed on biopsy not to be consistent with BCC.

Consistency of consecutive CT-scans, X-rays, or MRIs should be ensured during all assessments for each patient, with the same technique being used for evaluating lesions throughout the treatment period. (Use of spiral CT or MRI is required for baseline lesions <20 mm and must be documented in medical records and used consistently throughout the study.) The use of oral and IV contrast, etc., should be kept consistent as long as it is clinically possible. Tumor measurements should be made by the same Investigator/radiologist for each patient during the study to the extent that this is feasible.

In case of clinically measurable superficial lesions (such as skin), repeated photographs should be used to document tumor response. These photos must include a ruler for documentation purposes.

Tumor response will be confirmed a minimum of 4 weeks after the initial response was noted, or at the next scheduled tumor assessment if it is to occur more than 4 weeks after the initial response.

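### The SAP confirms responses at 23 days and labels this as 4 weeks or more, without reconciling it with the protocol's 4-week minimum, and it defines confirmed responders in two conflicting ways.

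*SAP*

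**What the plan says.** **Protocol.** Section 3.1 states that objective responses "should be confirmed by repeat assessments at least 4 weeks after initial documentation of response". Section 5.3.6 states: "Tumor response will be confirmed a minimum of 4 weeks after the initial response was noted". It adds one scheduling allowance: if the next planned assessment falls later than 4 weeks, confirmation may wait until then. The 4-week minimum also appears in the synopsis, Section 5.3.2 and footnotes 15 and 16 of Table 1. Table 1 schedules tumor assessment by physical examination "Every 4 to 8 weeks from the time of the first dose", and imaging every 8 to 16 weeks (8 weeks for newly enrolled metastatic patients). A ±5-day window applies around the scheduled visit (Table 1, Sections 5.3 and 5.3.6).

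**SAP, Best Response, programming notes.** Best overall response (BOR) is CR "if subject had CR on each of two tumor assessments which are greater than or equal to 23 days apart". It is PR if "the subject had two tumor assessments greater than or equal to 23 days apart with the response of the first assessment being PR"; either PR or CR will do at the later visit. Where other visits lie inside the pair, the PR rule accepts it "with either no other tumor assessments in between or the tumor response between these two assessments being CR, PR, or NE"; for CR, intervening visits may be CR or not evaluable (NE). One note then says that a patient whose BOR is CR or PR is a responder. The next note reads: "Best overall response rate is defined as the number of patients with a CR or PR observed at two consecutive assessments", with the gap given as 4 weeks or more and 23 days in brackets. The notes for duration of response, for both the table and the Kaplan-Meier plot, repeat the requirement of two consecutive assessments at 23 days or more.

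**The concern.** Protocol Section 8.2.1.1 calls ORR the efficacy variable of primary interest and duration of response the key secondary efficacy variable. Both depend on who counts as a confirmed responder. Assessment is by the investigator in an open-label, single-arm trial, and Appendix 1 of the protocol explains that confirmation guards against measurement error. Two things are unclear.

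- **The interval.** A reader of the results will take confirmed response to mean the protocol's 4 weeks or more, while the program will have used 23 days.
- **The pairing.** Two programmers working from the same SAP could include different patients in the ORR numerator and in the duration-of-response set.

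**Working it through.** **1. Where 23 comes from.** Direct conversion gives 4 × 7 = 28 days, not 23. Subtracting the 5-day window gives 28 − 5 = 23. The SAP's minimum time for stable disease fits the same pattern: 56 − 5 = 51 days. The origin is therefore very likely the window, although the SAP does not state it.

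**2. Whether the window implies 23.** The protocol places ±5 days around each scheduled visit. Two visits nominally 28 days apart can then be 28 − 10 = 18 to 28 + 10 = 38 days apart. If timing is uniform over the 11 × 11 = 121 pairs of days (an assumption):

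| Gap | Share |
|---|---|
| under 23 days | 15/121 = 12% |
| 23 to 27 days | 40/121 = 33% |
| 28 days or more | 66/121 = 55% |

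So 23 allows for one visit's window but not both. The only allowance in Section 5.3.6 for the confirmation gap lengthens it.

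**3. Who is affected by 23 versus 28 days.**

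- PR day 56, PR day 79, progressive disease (PD) day 107: the gap is 79 − 56 = 23 days. Confirmed at 23, not at 28.
- PR day 56, PR day 79, PR day 107: 107 − 56 = 51 days. Confirmed either way.

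Only patients whose sole qualifying pair is 23 to 27 days apart change status.

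**4. Size under a model.** Assumptions: 45–60% true responders; response onset uniform over days 20–150; exponential response duration with median 7.6 months (the earlier pivotal phase II trial) or 12.8 months (the phase I trial), both from Protocol Section 1.1.2.2; visit timing with SD 2 days, limited to ±5. A responder is confirmed if the first and last response assessments are at least 23 or at least 28 days apart. Difference in ORR, 23-day minus 28-day rule:

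| Schedule | Median 7.6 months | Median 12.8 months |
|---|---|---|
| 4-weekly | 1.4–1.9 points | 0.9–1.2 points |
| 5-weekly | 0.01–0.02 points | 0.01–0.02 points |
| 6- or 8-weekly | 0 | 0 |

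With uniform timing over the window the 4-weekly difference is 0.8–1.6 points. At 5 weeks a gap under 28 days needs the two visits to err by 8 days or more together, which is 6/121 = 5% of pairs against 33% at 4 weeks. The effect is then a few tenths of a point at most. At 6 weeks the shortest in-window gap is 42 − 10 = 32 days, so nobody changes.

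**5. Size without that model.** ORR falls by ORR × f, where f is the share of responders confirmed only at 23–27 days. Take n = 1119 (the locally advanced safety population in the SAP, an upper bound for those with measurable disease) and ORR 42.9% (locally advanced cohort of the pivotal phase II trial), giving 480 responders:

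| f | Responders left | Change in ORR |
|---|---|---|
| 1% | 475 | −0.4 points |
| 2% | 470 | −0.9 points |
| 5% | 456 | −2.1 points |
| 10% | 432 | −4.3 points |

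At f = 5% the Clopper-Pearson interval moves from 40.0–45.9% to 37.9–43.7%. The documents give neither f nor the number with measurable disease. The 10% row shows sensitivity only and is not an expectation.

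**6. The two pairing rules, with the interval held at 23 days.**

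| Sequence | BOR rule | Consecutive rule |
|---|---|---|
| PR day 56, NE day 84, PR day 112 | responder | not |
| PR day 56, PR day 70, PR day 84 | responder | not (each step is 14 days) |
| CR day 56, PR day 84, PD day 112 | not | responder, if any CR/PR mixture is allowed |

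The first two rows are plain conflicts. The third depends on how the rate sentence is read.

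**The case against.** **The 23 days is principled.** It equals the protocol's interval less the protocol's own window, and the stable-disease minimum is built the same way. Protocol Appendix 1 describes confirmation as generally 4 weeks later. This stands as an explanation of origin. It does not settle the matter, because the main text of the protocol sets a minimum and never applies the window to it. The SAP neither explains the figure nor declares a departure.

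**A strict 28 days has its own cost.** With timing SD of 2 days, about 43% of on-schedule 4-weekly gaps are under 28 days, so some in-window confirmations would fail by chance. This stands, and it is why the choice of main rule is open to argument.

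**The SAP already names the responder.** It does say that BOR of CR or PR makes a responder, and Protocol Section 8.2.1.1 defines the rate in the same way. A reader might infer that the CR and PR rows will not add up to the responder row. That does not follow if the program uses the BOR sentence. What remains is a competing definition in the rate note and both duration-of-response notes.

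**CR followed by PR.** A reader might infer that such a patient is wrongly counted. That needs the rate sentence to allow a mixture, which is one reading only. Table 3 of Protocol Appendix 1 gives PR there only if the original CR is relabelled, and the SAP's BOR rule is compatible with that.

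**Impact is limited.** ORR is a secondary, descriptive variable in a safety study with no hypothesis test (Protocol Sections 8.1 and 8.2). This stands.

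**Conclusion.** The mismatch is real and should be resolved. The protocol's floor is 4 weeks, and the SAP accepts 23 days while describing it as 4 weeks or more. The SAP can therefore count a responder who fails the literal protocol minimum. Under the stated assumptions this is worth roughly 0.8 to 1.9 points of ORR if all assessments are 4-weekly, and almost nothing at 5-weekly or longer. The protocol permits 4 to 8 weeks by examination and longer by imaging, and the documents do not give the mix of schedules actually used, so these are upper figures.

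A reader might infer that the reported ORR is inflated by 1 to 2 points, or that 23 days is an arbitrary relaxation. The documents support neither. The figure matches the assessment window, and the number of patients confirmed only at 23–27 days is unknown.

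The pairing conflict is separate. It leaves the ORR numerator and the duration-of-response set ambiguous, but it does not by itself raise ORR: in the clear cases the consecutive rule removes patients. The protocol does not require the two assessments to be consecutive.

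**What to change.** 1. Define the ORR numerator and the duration-of-response set as patients whose BOR is confirmed CR or PR under the SAP's BOR rule. Delete the wording about two consecutive assessments from the rate note and from the duration-of-response table and plot notes. Time to response should use the same set.
2. Stop presenting 23 days as 4 weeks or more. Either apply the protocol's 28-day minimum, or keep 23 days and state it as a declared departure that uses the 5-day window.
3. In either case, report ORR and duration of response under both 28 and 23 days, and give the number of responders confirmed only at 23–27 days. That count answers the question of size directly.

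The cost is a short SAP revision and one extra run. The 28-day ORR may be slightly lower, partly because some in-window 4-weekly visits fall less than 28 days apart. Duration of response may move the other way, because patients who drop out of the 28-day set tend to have short or early-censored responses.

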6. INVESTIGATIONAL MEDICINAL PRODUCT (IMP)

6.1 DOSE AND SCHEDULE

Enrolled patients will receive continuous once-daily oral dosing of vismodegib at a dosage of 150 mg per administration. One cycle of therapy is defined as 28 days of treatment. Dose reduction of vismodegib is not permitted, as there is only a 150-mg capsule strength available.

Dosing of vismodegib will continue until one of the following occurs:

- Investigator-assessed disease progression
- Unacceptable toxicities most likely attributable to vismodegib
- Patient consent withdrawal
- Death
- Reasons deemed by the treating physician
- Study termination by the Sponsor

If there is objective evidence of progressive disease, but the Investigator believes the patient is still deriving benefit from treatment, treatment with vismodegib may be continued after consultation with the medical monitor. However, if there is evidence of further disease progression at the next tumor assessment, vismodegib should be discontinued.

At each study visit, patients will be given enough capsules for dosing until the next study visit. The Investigator is required to confirm that any female patient of childbearing potential has a negative pregnancy test, understands the teratogenic potential of vismodegib, and is using an effective method of contraception prior to dispensing vismodegib. Patients will be instructed to take one 150 mg capsule per day.

Vismodegib should be taken at approximately the same time each day, with or without food. Capsules must be swallowed whole and must not be opened under any circumstances. If a patient misses a dose (e.g., due to emesis), he or she should be instructed not to take or make up that dose and to resume dosing with the next

scheduled dose. Missed doses will not be made up. Patients will be instructed to bring all unused capsules to each study visit for assessment of compliance.

If a patient is suspected to be pregnant, vismodegib must be immediately discontinued. If it is subsequently confirmed that the patient is not pregnant, dosing may be resumed.

The terminal half-life of vismodegib has been determined to be 10–14 days in humans, based on preliminary findings in healthy patients. If plasma concentrations of vismodegib need to be lowered emergently, animal studies suggest that oral administration of activated charcoal may lower plasma drug levels more quickly than dose cessation alone.

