### Programming Note:

- Duration of response will be calculated only for patients whose confirmed best response is CR or PR.
- Duration of response is the interval between the Date of First Response and the Date of Progressive Disease or Death, and is calculated only for patients with confirmed best response of CR or PR at two consecutive assessments  $\geq 23$  days.
- Patients without Progression of Disease or Death will be censored at the date of last tumour assessment and the duration of response is calculated using the interval between Date of First Response and the date of last tumour assessment.
- N would be the number of patients with a measurable or non-measurable disease at baseline and histologically confirmed BCC.
- Percentages are based on the number of patients with a measurable disease at baseline and histologically confirmed BCC, and who had a CR or PR.
- Duration of response will be calculated in Months.

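### The SAP's best-overall-response rules do not clearly exclude a CR or PR confirmed only after first progression, so SD–PD–PR–PR can count as a response while PD–PR–PR does not

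*SAP*

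**What the plan says.** The rules are in the SAP, Output Specifications: Efficacy Tables, Best Response, item 1, Programming Notes.

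- **CR:** the rule applies "if subject had CR on each of two tumor assessments which are greater than or equal to 23 days apart", and otherwise restricts only what lies between those two assessments.
- **PR:** the rule has the same form, "with either no other tumor assessments in between or the tumor response between these two assessments being CR, PR, or NE".
- **SD:** this is the only category rule with its own PD condition. It needs an assessment of "CR, PR or SD with minimum of 51 days after First Dose Date without any Progressive Disease (PD) in between". It ranks below response: "Best Overall Response would be Stable Disease (SD) if subject's best overall response is not CR or PR".
- **PD override:** "BOR would be PD if PD occurred before satisfying any of the above criteria of Best Overall Response".
- **Response rate:** the definition counts patients with CR or PR at two consecutive assessments and carries no PD condition.

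On duration, the SAP's Programming Note says "Duration of response is the interval between the Date of First Response and the Date of Progressive Disease or Death" and censors only patients with no progression or death. Protocol 8.2.1.1 also ends duration at PD or death, but its censoring sentence looks only at progression occurring after the response that qualifies.

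On whether assessments after PD can exist, Protocol 6.1 says that where the investigator still sees benefit despite objective progression, "treatment with vismodegib may be continued after consultation with the medical monitor". It also refers to a next tumor assessment.

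**The concern.** A PD guard was written into the SD rule and not into the CR or PR rules. The override appears meant to cover the gap, but its condition is that PD came before any criterion was satisfied. A patient with SD at day 51 or later has already satisfied one. A PD after that does not trigger the override, and a still later confirmed PR outranks SD.

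Protocol 8.2.1.1 names ORR as the efficacy variable of primary interest and duration of response as the key secondary one. The same patient could be a PFS event on one date and a new responder on a later date. Two programmers could also code the same record differently and both claim to follow the text.

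**Working it through.** **No figure to reproduce.** The documents give no ORR, duration or count of post-PD responders for this trial. The SAP's day limits do fit the protocol's intervals and ±5-day window: 28 − 5 = 23 and 56 − 5 = 51.

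**Rules applied to example records** (days from first dose; 8-week spacing as in Protocol 3.1 for later metastatic patients, closer in some rows):

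| Record | SAP read literally | Cut at first PD |
|---|---|---|
| SD 56, PD 112, PR 168, PR 224 | PR | SD |
| SD 56, PD 112, CR 168, CR 224 | CR | SD |
| PD 28, PR 56, PR 112 | PD | PD |
| SD 28, PD 42, PR 84, PR 112 | PD | PD |
| SD 56, PR 112, PR 168, PD 224 | PR | PR |

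The first two rows change. In row 4 the SD came before day 51, so the override still applies.

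**Duration in the first row**, dated from the first of the confirming pair:
- SAP wording with the only PD date: 112 − 168 = −56 days.
- Protocol censoring wording: alive, no progression after day 168, last assessment day 224, so censored at 224 − 168 = +56 days.
- Time to response is 168 days, while PFS is an event at 112 days.

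**Direction of the effect.** Take all 4⁵ = 1,024 sequences of CR, PR, SD and PD over five visits 56 days apart. Compare the literal rules with the same rules cut at first PD.
- First PD at visit 2: 3 non-PD results at visit 1 × 20 of the 64 three-visit continuations that contain a confirming pair = 60.
- First PD at visit 3: 6 of the 9 non-PD openings have no confirmed response yet, × 3 confirming pairs = 18.
- Total 60 + 18 = 78 sequences gain a response. None loses one.
- In 9 of the 78 (3 × 3: PD at visit 2, pair at visits 3–4, PD at visit 5) a second PD follows the response. In the other 69 every PD precedes it.

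These are unweighted combinations. They show direction, not frequency.

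**Can target lesions produce such a record?** Under Appendix 1, section 2.3.1, PD is judged from nadir and PR from baseline. Illustrative sums of 100, 75, 90 and 68 mm give:
- 75 mm: −25% from baseline, SD.
- 90 mm: 90/75 = +20% and +15 mm from nadir, PD.
- 68 mm: −32% from baseline, PR.

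**Size.** With m patients in the ORR denominator, k affected patients add 100·k/m points. Neither k nor m is in the documents. Two assumed cases:
- m = 1,000 with 600 true responders (60.0%, exact 95% CI 56.9–63.1): k = 5, 10, 20 or 50 gives 60.5%, 61.0%, 62.0% or 65.0%.
- m = 80 with 28 true responders (35.0%, CI 24.7–46.5): k = 1, 2 or 4 gives 36.25%, 37.5% or 40.0%.

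**The case against.** **The override can be read the other way.** SD is open only to patients who are not CR or PR, so it can be seen as a residual category judged on the whole record, not as a milestone reached at day 56. In SD–PD–PR–PR the only criterion then satisfied is PR, on day 224. PD came first, the override applies, and the patient is a non-responder. This reading also gives the override a purpose. It stands as a possible reading. It is less natural, because it labels as PD a patient who met the SD condition before progressing. The result is that one record can be PR or PD under the present text, and SD under a first-PD cut.

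**The protocol already handles duration.** Its censoring sentence avoids the negative value. That stands, and the remaining defect is the SAP's shorter wording.

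**Such patients should be rare.** This largely stands.
- Treatment beyond PD is an exception and stops on further progression at the next assessment.
- Table 1 of the protocol shows no tumor assessment in the safety follow-up column.
- The SAP's mock lesion listing shows a PD as that patient's last row, with treatment ended.
- Progression by a new lesion is a weak route to a later PR, because Appendix 1, section 2.4.1 makes any time point with a new lesion PD.

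Against this, the protocol's account of the earlier pivotal study counts responses after onset of progression in its clinical benefit rate, so the pattern is known in this programme.

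**A filter may exist elsewhere.** The SAP defers some derivations to the DAP M3 and the LoPO, which are not available here. It cites neither for a cut at PD in these rules.

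**The stakes are limited.** Safety is the primary objective, and Protocol 8.2 plans no formal test. That stands and sets the priority.

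**Conclusion.** The rules are incomplete and open to two readings. On the more literal one, a CR or PR confirmed only after PD counts as a response, provided SD was met first. PD–PR–PR is excluded by the override, although the response-rate definition taken alone would count it too. Any effect on ORR can only be upward. It is probably small, since treatment beyond PD is exceptional, but the documents do not allow it to be estimated.

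Two stronger conclusions are tempting and are not supported:
- A reader might infer that the reported ORR is inflated. The documents show neither how the override was programmed nor that any affected patient exists.
- A reader might infer that the plan yields negative durations as a matter of course. That needs a patient of this kind, the SAP's shortened wording and use of the PD date before the response. The protocol's censoring wording avoids it.

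This should be fixed, but it does not threaten the trial's main purpose, because ORR is a descriptive secondary variable. The conclusion assumes that no unseen specification already discards assessments after first PD.

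**What to change.** 1. In the Best Response Programming Notes, state that only assessments up to and including first PD are used to derive best overall response, and that both assessments confirming a CR or PR must precede first PD. Put the same condition in the response-rate definition.
2. Use the same cut for the date of first response in duration of response and time to response.
3. Align the duration-of-response notes (table and Kaplan-Meier plot) with Protocol 8.2.1.1, so that the event is the first PD or death after the qualifying response.
4. Flag responses after PD in the lesion listing only, outside ORR and duration of response.

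If the DAP M3 already holds such a cut, a cross-reference would do. The cost is a sentence or two and one filter in the derivation. No new data are needed. ORR may fall slightly.
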